Appendix 2. Schedule of Activities

Schedule of Activities, Protocol I1F-MC-RHBQ

CRF Visit (V) Number	Screening		Baseline Randomization	Blinded Treatment Period (Period 2)				
	V1		V2	V3	V4	V5	V6	V7
Weeks since Randomization			W0	W1	W2	W4	W8	W12
Study Days	-30 to -7 d	V1A: 2-3 d post-V1	1	7 ± 2d	14 ± 2d	28 ± 2d	56 ± 2d	84 ± 4d
Informed consent	X							
Complete medical history	X							
Demographics ^a	X							
Sociodemographics ^b			X					X
Physical examination ^c	X		X					X
Perianal/gluteal cleft characteristics examination	X		X					X
Inclusion/exclusion criteria ^d	X		X					
Body temperature			X					
Height			X					
Weight			X					X
Waist circumference			X					
Vital signs (BP and pulse)	X		X ^e	X	X	X	X	X ^e
Consumption habits ^f			X					
Concomitant medications	X		X	X	X	X	X	X
Review preexisting conditions/AEs			X	X	X	X	X	X
Randomization			X					
Administer IP on site			X					X

	Screening		Baseline Randomization	Blinded Treatment Dosing Period (Period 2)				
CRF Visit (V) Number	V1		V2	V3	V4	V5	V6	V7
Weeks since Randomization			W0	W1	W2	W4	W8	W12
Study Days	-30 to -7 d	V1A: 2-3 d post-V1	1	7 ± 2d	14 ± 2d	28 ± 2d	56 ± 2d	84 ± 4d
Dispense IP			X		X	X	X	X
Provide SDALg			X		X	X	X	X
Collect, review, and enter data from SDAL			X		X	X	X	X
Review e-diary				X	X	X	X	X
Dispense e-diary (includes GPSS, GPSIS, and SFQ)	X							
Collect e-diary								X
Clinical Efficacy/Health Outcomes								
sPGA (overall)	X		X	X	X	X	X	X
sPGA of Genitalia ^h	X		X	X	X	X	X	X
PASI (overall)	X		X	X	X	X	X	X
mGPASI ⁱ	X		X	X	X	X	X	X
BSA	X		X ^j	X	X	X ^j	X	X ^j
Fitzpatrick skin type			X					
GPSS ^k	Daily from Screening (V1) to Week 12 (V7)							X
GPSIS ^k	Weekly from Screening (V1) to Week 12 (V7)							X
SFQ ^k	Weekly from Screening (V1) to Week 12 (V7)							X
PatGA-Genital			X	X	X	X	X	X
Touch avoidance NRS			X		X	X	X	X

CRF Visit (V) Number	Screening		Baseline Randomization	Blinded Treatment Dosing Period (Period 2)				
	V1		V2	V3	V4	V5	V6	V7
Weeks since Randomization			W0	W1	W2	W4	W8	W12
Study Days	-30 to -7 d	V1A: 2-3 d post-V1	1	7 ± 2d	14 ± 2d	28 ± 2d	56 ± 2d	84 ± 4d
SF-36			X					X
DLQI			X		X	X	X	X
QIDS-SR16	X		X					X
C-SSRS [§]			X	X	X	X	X	X
Self-Harm Supplement Form [§]			X	X	X	X	X	X
CAPP (genital subindex)			X					X
Laboratory Tests								
Administer PPD/QuantiFERON [®] -TB Gold/T-SPOT [®] 1	X							
Read PPD		X						
Chest x-ray ^m	X							
ECG	X							
HIV/HCV	X							
HBV ⁿ	X		X					X
FSH ^o	X							
Serum pregnancy test ^p	X							

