GPSS	
The Genital Psoriasis Symptoms Scale (GPSS) is a patient-administered assessment of 8 symptoms: itch, pain, discomfort, stinging, burning, redness, scaling, and cracking. Respondents are asked to answer the questions based on their psoriasis symptoms in the respective genital areas.
 
The overall severity for each individual symptom from patient's genital psoriasis is indicated by selecting the number from an NRS of 0 to 10 that best describes the worst level of each symptom in the genital area in the past 24 hours, where 0 (= no severity) and 10 (worst imaginable severity).
 
The symptom severity scores, ranging from 0 to 10, are the values of the selected numbers indicated by the patient on the instrument's horizontal scale. Each of the 8 individual items will receive a score of 0 to 10 and will be reported as item scores for itch, pain, discomfort, stinging, burning, redness, scaling, and cracking. In addition, a total score ranging from 0 (no genital psoriasis symptoms) to 80 (worst imaginable genital psoriasis symptoms) will be reported.
	GPSS total score	
The GPSS total score will be calculated by summing the individual item scores as follows: GPSS = itch NRS + pain NRS + discomfort NRS + stinging NRS + burning NRS + redness NRS + scaling NRS + cracking NRS
 
The GPSS total score at Week 12 (Visit 7) is the average of at least 4 non-missing scores of the last 7 consecutive days. The 7-day window ends on the date of Visit 7 when the data is collected on site, and on or after the date of previous visit.
 
The GPSS total score at Week 2 (Visit 4), Week 4 (Visit 5), and Week 8 (Visit 6), is the average of at least 4 non-missing scores of the last 7 consecutive days before the date of current visit, and on or after the date of previous visit.
 
The GPSS total score at Week 1 (Visit 3), the 7-day window is before the date of Visit 3, and on or after the date of the first injection.
 
Note 1: For derivations of post-baseline visit scores, when there are less than 4 non-missing scores in the 7-day window, the window will be extended one day at a time, up to 10 days, until 4 non-missing scores are found, but the window will not be extended beyond the date of previous visit. If at least 4 non-missing scores are still not found, the visit score will be designated as missing.
 
Note 2: When 7-day duration is not present between visits, the visit score will be the average of at least 4
	If any item score is missing, the GPSS total score will be missing.

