
Measure	Description	Variable	Derivation	Imputation Approach if Components are Missing
			
non-missing scores prior to current visit, and on or after previous visit. If at least 4 non-missing scores are not found, the visit score will be designated as missing.
 
For the visit beyond Week 12 (Visit 7), the score is as being collected at that visit on site.
 
As exploratory analyses, GPSS total score at each calendar week in the Blinded Treatment Period is examined, and defined as the average of 4 or more non-missing scores collected within the week. If at least 4 non-missing scores are not found during the calendar week, the score at that week is designated as missing.
 
The calendar week is defined as follows: Calendar Week 1 is from study day 1 to 7; Calendar Week 2 is from study day 8 to 14; ... Calendar Week 11 is from study day 70 to 77; Calendar Week 12 is from study day 78 to the date of Visit 7.
 
Note that study day 1 is the date of the first injection during the Blinded Treatment Period.
	
		GPSS change from baseline	
Change from baseline $= \text{Observed GPSS Total score} - \text{Baseline GPSS total score}$
 
A negative change indicates improvement and a positive change indicates deterioration of the condition.
	Missing if either observed or baseline GPSS total score is missing

Measure	Description	Variable	Derivation	Imputation Approach if Components are Missing
		GPSS item score	
For each GPSS item, the score at each post-baseline visit in the Blinded Treatment Period and Open-Label Treatment Period, is derived in the same manner as GPSS total score.
 
For each GPSS item, the score at each calendar week in the Blinded Treatment Period, is derived in the same manner as GPSS total score.
	Missing if the GPSS item score is missing
		Change from baseline for each GPSS item	
Change from baseline $= \text{Observed NRS score} - \text{Baseline NRS score}$
 
A negative change indicates improvement and a positive change indicates deterioration of the condition.
	Missing if either observed or baseline GPSS item score is missing

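### SAP Table RHBQ.6.4 starts Calendar Week 11 a day early, and its variable-length Week 12 can make an in-window patient an automatic failure in the exploratory weekly itch-response analysis

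*SAP*

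**What the plan says.** SAP Section 6.10, Table RHBQ.6.4, defines calendar weeks for exploratory analyses of the diary scales. The list begins "Calendar Week 1 is from study day 1 to 7" and "Calendar Week 2 is from study day 8 to 14", skips to Week 11 with an ellipsis, and ends with "Calendar Week 11 is from study day 70 to 77" and "Calendar Week 12 is from study day 78 to the date of Visit 7". The day count starts at the first injection: "Note that study day 1 is the date of the first injection during the Blinded Treatment Period". The same ranges appear in the GPSS, GPSIS and SFQ derivations.

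For the GPSS calendar-week score, the table says: "If at least 4 non-missing scores are not found during the calendar week, the score at that week is designated as missing". The item scores, including itch, follow the rule for the total score. Note 1 in the same table lets a window grow backward by a day at a time, up to 10 days, but its scope is limited: "For derivations of post-baseline visit scores, when there are less than 4 non-missing scores in the 7-day window".

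Table RHBQ.6.5 analyses the 3-point itch response at each calendar week, in patients with a baseline score of at least 3, by logistic regression and Fisher's exact test with NRI, and labels these rows exploratory. Under SAP Section 6.3.1 a patient with missing response data is a treatment failure. Protocol Appendix 2 schedules Visit 7 at study day 84 ± 4, with Visit 2 as day 1.

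**The concern.** There are two separate points.

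First, the Week 11 start breaks the seven-day pattern, so one diary day belongs to two weeks. This is an operative derivation rule that a programmer would code as written.

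Second, the length of Week 12 depends on when Visit 7 takes place, while the minimum of 4 daily scores is fixed. At the early end of the permitted visit window there are not enough days to meet the minimum, however complete the diary. NRI then turns that missing score into a failure. The same patient's Visit 7 itch score looks back 7 days and can be computed, so one report could show the patient as a responder for the Visit 7 itch endpoint and a non-responder at calendar Week 12.

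**Working it through.** **Week boundaries.** Seven-day blocks from day 1 put week k at days 7(k − 1) + 1 to 7k.

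- k = 1 gives 1–7 and k = 2 gives 8–14, both as stated.
- k = 12 starts at 7 × 11 + 1 = 78, as stated.
- k = 11 gives 7 × 10 + 1 = 71 to 77. The SAP states 70 to 77, which is 77 − 70 + 1 = 8 days.
- k = 10 gives 64–70, so day 70 is in both weeks. Week 10 is not written out. If it were meant to end on day 69 it would have 6 days, so the list is irregular on either reading.

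**Length of Week 12.** With Visit 7 on study day v, the length is v − 78 + 1. The literal window is 84 − 4 = 80 to 84 + 4 = 88.

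| Visit 7 (study day) | 80 | 81 | 82 | 83 | 84 | 85 | 86 | 87 | 88 |
|---|---|---|---|---|---|---|---|---|---|
| Days in Week 12 | 3 | 4 | 5 | 6 | 7 | 8 | 9 | 10 | 11 |

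**Chance of a missing GPSS score at calendar Week 12.** The last day of Week 12 is Visit 7, when the scale is completed on site. Take that entry as present. Then at least 3 of the remaining (length − 1) home-diary days are needed. The documents give no diary completion rate. I assume 90% or 80% per day, with days independent.

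- Day 80: 2 home days, 3 needed. Always missing.
- Day 81: all 3 home days needed. 1 − 0.9³ = 1 − 0.729 = 27%; 1 − 0.8³ = 1 − 0.512 = 49%.
- Day 82: at least 3 of 4. At 90%: 1 − (0.9⁴ + 4 × 0.9³ × 0.1) = 1 − (0.6561 + 0.2916) = 5%. At 80%: 1 − (0.8⁴ + 4 × 0.8³ × 0.2) = 1 − (0.4096 + 0.4096) = 18%.
- Day 84: at least 3 of 6. Below 2% at either rate.

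**Same patient, Visit 7 score.** For a day-80 visit the Visit 7 GPSS window is the 7 days ending on day 80, that is days 74–80, and Note 1 allows extension. The score is evaluable with an ordinary diary.

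**Other reading of the window.** The schedule gives visits as 7 × week (7, 14, 28, 56, 84) while calling baseline day 1. If 84 ± 4 means days after day 1, Visit 7 falls on study days 81–89. Week 12 is then 81 − 78 + 1 = 4 to 89 − 78 + 1 = 12 days long, and no in-window patient is forced to fail.

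**The case against.** The strongest reply is that the first point is probably a typing error with little effect: one extra day enters an average of up to 8 daily scores, and calendar weeks are never added together. That stands as to size. It does not remove the need to correct a rule that is repeated three times.

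The reply to the second point is that ending Week 12 at Visit 7 is a sensible design choice. The diary is collected there and open-label dosing begins, so the end must move with the visit. That also stands. The fault lies in pairing a movable end with a fixed minimum of 4 scores and no extension, not in the movable end itself.

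A reader might go further and infer that many patients are failed by construction, that the weekly curve is materially distorted, or that a treatment comparison is biased. The documents do not support this. Failure is certain only for day 80, one of nine permitted days on the literal reading (or an earlier, out-of-window visit). They give no distribution of Visit 7 days, and nothing in them suggests early visits would differ by arm.

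Nor does the problem reach the confirmatory results. The itch endpoint in the testing sequence uses its own Visit 7 look-back with extension. GPSIS and SFQ take the last non-missing score in the week, and the on-site Visit 7 score falls inside Week 12, so they are not forced to missing. In the calendar-week MMRM of GPSS change, the affected patients are missing, not failures.

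**Conclusion.** The calendar-week rule is wrong as written, with consequences confined to exploratory outputs.

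The Week 11 start should be day 71; this follows from the SAP's own pattern and needs no assumption beyond the ellipsis meaning seven-day weeks. The 3-to-11-day span of Week 12, and the certain failure for a day-80 visit in the weekly itch-response analysis, follow from the SAP rules and the literal reading of the visit window. On the days-after-day-1 reading the span is 4 to 12 days and certain failure disappears, though a day-81 visit still needs a complete set of 4 entries.

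The percentages for days 81 and 82 are illustrations that depend on the assumed completion rates, on independent days and on the on-site entry being present. The number of patients affected cannot be derived from the documents. The primary and major secondary endpoints are unaffected.

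**What to change.** 1. Change 70 to 71 in the GPSS, GPSIS and SFQ derivations in Table RHBQ.6.4, and write out Week 10 as days 64–70.
2. Keep Week 12 as day 78 to Visit 7. For GPSS only, when fewer than 4 scores are present, apply Note 1's backward one-day-at-a-time extension, up to 10 days, to calendar Week 12. State that this may reuse Week 11 days. For a day-80 visit with a complete diary it adds day 77 alone.
3. State whether 84 ± 4 means study days 80–88 or 81–89.

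Redefining Week 12 as the 7 days ending at Visit 7 is less suitable. A day-80 visit would give days 74–80 and share days 74–77 with corrected Week 11. A day-88 visit would give days 82–88 and leave days 78–81 in no week.

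The cost is a few words in the SAP and a small change to the calendar-week program. No confirmatory analysis, data collection or sample size changes.

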8.1.2.2.3. Sexual Frequency Questionnaire

The SFQ is a patient reported outcome measure to evaluate the impact of genital psoriasis symptoms on sexual frequency. It consists of 2 items that assess the impact of genital psoriasis symptoms on the frequency of sexual activity. Respondents are asked to answer the questions based on their psoriasis symptoms in the genital area. Genital area is defined as the labia majora (outer lip), labia minora (inner lip), and perineum (area between vagina and anus) for females; penis, scrotum, and perineum (area between the penis and anus) for males. The definition of sexual activity is not limited to intercourse and includes activities such as masturbation.

Item 1 asks how many times the patient engaged in sexual activity in the past week with response options of none/zero (2), once (1), and two or more (0).

Item 2 assesses how often genital psoriasis symptoms limited the frequency of sexual activity with response options ranging from 0 (never) to 4 (always).

The individual item scores of the SFQ are reported separately. No total score is calculated for the SFQ.

The instructions for completion are embedded within the SFQ questionnaire for patients to read before responding to the items. Prior to Week 12 (Visit 7), patients will use an e-diary, using a recall period of 1 week, and the response for each item uses a Likert scale. Thereafter, study participants will answer these questions only at scheduled study visits using the same 1-week recall period as used for the e-diary.

SFQ individual item scores at Week 12 (Visit 7) are the scores collected at Visit 7 on site.

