6.1.2. Baseline Definition

Unless otherwise specified, for efficacy and health outcomes analyses in the Blinded and Open-label Treatment periods, baseline will be defined as the last available value before the first injection of the investigational product. In most cases, this will be the measurement recorded at Week 0 (Visit 2). For efficacy measures, if the patient does not take any injection, the last available value on or prior to randomization date will be used.

Unless otherwise specified for safety analyses in the Blinded Treatment Period, baseline will be defined as the last available value before the first injection of the investigational product. In most cases, this will be the measurement recorded at Week 0 (Visit 2). For safety analyses using a baseline period, the baseline period is defined as the time from Visit 1 to the date/time of the first injection.

Unless otherwise specified, the baseline for safety analyses in the Open-label Treatment Period is defined as the last non-missing assessment on or prior to Week 12 (Visit 7) and prior to the first injection of the open-label investigational product at Visit 7.

Unless otherwise specified, the baseline for safety analyses in the Post-Treatment Follow-up Period is defined as the last non-missing assessment on or prior to Week 52 (Visit 12) or ETV.

For each Genital Psoriasis Symptoms Scale (GPSS) item score and the total score, the baseline for efficacy analyses in the Blinded and Open-label Treatment Period is defined as the average of 4 or more non-missing assessments collected during the last 7 consecutive days, prior to the date of the first injection, that is, the sum of the assessments divided by the number of days on which the assessment is completed. When there are <4 non-missing assessments in the 7-day window, the window will be extended towards the date of Visit 1, until 4 daily non-missing assessments are found. However, if there are not at least 4 non-missing assessments collected prior to the date of the first injection, the baseline will be designated as missing.

For Genital Psoriasis Sexual Impact Scale (GPSIS) subscale scores and Sexual Frequency Questionnaire (SFQ) item scores, the baseline for efficacy analyses in the Blinded and Open-label Treatment Period is defined as the last non-missing assessment collected prior to the date of the first injection.

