GPSIS	
The GPSIS is a patient reported outcome measure to evaluate the impact of genital psoriasis symptoms on sexual activity. The GPSIS consists of 3 items that include 2 subscales:
 
 Sexual Activity Avoidance Subscale: This subscale includes items 1 and 2. Item 1 asks whether the patient has been sexually active in the past week. Item 2 asks how often the patient avoided sexual activity in the past week due to Genital Ps. Impact of Sexual Activity on Genital Psoriasis Symptoms Subscale: This subscale includes item 1 and 3. Item 1 asks whether the patient has been 	GPSIS Sexual Activity Avoidance Subscale score	
For Item 1, if a patient selects “no due to reasons other than my genital psoriasis”, they do not answer any additional questions on the scale and receive a score of 1 on the Sexual Activity Avoidance Subscale. If a patient responds “no due to my genital psoriasis” on GPSIS Item 1, the subscale score is set to “5” (equivalent to always avoid sexual activity due to genital psoriasis on item 2).
 
For patients who are sexually active (i.e. with a score of 0 on Item 1), a response of never, rarely, sometimes, and often on item 2 receive a score of 1, 2, 3, and 4, respectively, on the Sexual Activity Avoidance Subscale.
 
The Sexual Activity Avoidance Subscale ranges from 1 (never) to 5 (always) avoid sexual activity.
 
The Avoidance Subscale Score at Week 12 (Visit 7) is the subscale score collected at Visit 7 on site.
 
The Sexual Activity Avoidance Subscale Score at Week 2 (Visit 4), Week 4 (Visit 5), and Week 8 (Visit 6) is defined as the last non-missing subscale score collected before the date of the visit, and on or after the date of previous visit.
 
The Avoidance Subscale score at Week 1 (Visit 3) is the last non-missing subscale score before the date of Visit 3 and on or after the date of the first injection.
 
For the visit beyond Week 12 (Visit 7), the score is as being collected at that visit on site.
 
For exploratory analyses, GPSS total score at each calendar week in Blinded Treatment Period is
	
The Sexual Activity Avoidance Subscale score is missing if: Item 1 is missing; or Item 1 is answered as “Yes” but Item 2 is missing

Measure	Description	Variable	Derivation	Imputation Approach if Components are Missing

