SFQ	
The SFQ is a patient reported outcome measure to evaluate the impact of genital psoriasis symptoms on sexual frequency. It consists of 2 items that assess the impact of genital psoriasis symptoms on the frequency of sexual activity. Respondents are asked to answer the questions based on their psoriasis symptoms in the genital area.
 
Item 1 asks how many times the patient engaged in sexual activity in the past week with response options of: 2 = none/zero 1 = once 0 = two or more
 
Item 2 assesses how often genital psoriasis symptoms limited the frequency of sexual activity with the following response options: 0 = never 1 = rarely 2 = sometimes 3 = often 4 = always
	SFQ Item 1	
Item 1 score as reported in the weekly e-diaries. The score ranges from 0 to 2.
 
Item 1 Score at Week 12 (Visit 7) is the score collected at Visit 7 on site.
 
Item 1 Score at Week 2 (Visit 4), Week 4 (Visit 5), and Week 8 (Visit 6) is defined as the last non-missing score collected before the date of the visit, and on or after the date of previous visit.
 
Item 1 Score is the lasting non-missing score before the date of Visit 3 and on or after the date of the first injection.
 
For the visit beyond Week 12 (Visit 7), the score is as being collected at that visit on site.
	Missing if the item 1 score is missing
		SFQ Item 2	
Item 2 score as reported in the weekly e-diaries. The score ranges from 0 to 4.
 
Item 2 Score, at each post-baseline visit in the Blinded Treatment Period and Open-Label Treatment Period, is derived in the same manner as Item 1 Score.
	Missing if the item 2 score is missing

Measure	Description	Variable	Derivation	Imputation Approach if Components are Missing
	The individual item scores of the SFQ are reported separately. No total score is calculated for the SFQ.		
For exploratory analyses, Item 2 Score at each calendar week is examined, and defined as the last non-missing subscale score collected in the calendar week.
 
The calendar week is defined as follows: Calendar Week 1 is from study day 1 to 7; Calendar Week 2 is from study day 8 to 14; ... Calendar Week 11 is from study day 70 to 77; Calendar Week 12 is from study day 78 to the date of Visit 7.
 
Note that study day 1 is the date of the first injection during the Blinded Treatment Period.
	
		SFQ Item 2 Score of 0 or 1	Item 2 score is assessed as 0 or 1.	Missing if the item 2 score is missing

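### Day 1 diary entries are assigned by date, not by time of dosing, so a pre-dose entry is kept out of baseline and can be scored as a Week 1 outcome

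*SAP*

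**What the plan says.** SAP 6.1.2 gives the diary scales their own baseline. For GPSIS and SFQ it is "the last non-missing assessment collected prior to the date of the first injection". The GPSS baseline is an average of daily entries that also stops before the injection date.

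SAP Table RHBQ.6.4 then opens the first post-baseline window on the date that baseline excludes:

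- GPSIS, Week 1: "the last non-missing subscale score before the date of Visit 3 and on or after the date of the first injection".
- SFQ, Week 1: "the lasting non-missing score before the date of Visit 3 and on or after the date of the first injection".
- GPSS, Week 1: "the 7-day window is before the date of Visit 3, and on or after the date of the first injection", averaging at least 4 daily scores. If entries are short the window may be lengthened, but "the window will not be extended beyond the date of previous visit".
- Exploratory weeks: "Calendar Week 1 is from study day 1 to 7", with study day 1 defined as the first-injection date.

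On recall, Protocol 8.1.2.2.1 gives the daily GPSS a 24-hour period. For the weekly SFQ, Protocol 8.1.2.2.3 says "patients will use an e-diary, using a recall period of 1 week", and 8.1.2.2.2 does the same for the GPSIS. The first dose is given in clinic at Visit 2 (Protocol 6.1). I found no rule that separates Day 1 entries made before the injection from those made after it.

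**The concern.** A diary entry made on the morning of randomisation, before the first injection, describes an untreated patient and is the most recent pre-dose value available. The rules discard it as baseline and accept it as outcome. In the GPSS it enters the Week 1 average. In a weekly scale it can be the Week 1 score itself.

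These time points are tested. Table RHBQ.6.5 applies logistic regression with NRI to itch response, SFQ Item 2 and GPSIS at every post-baseline visit and calendar week, and MMRM to GPSS change. Untreated content in the Week 1 score moves both arms towards their pre-dose level, so the estimated difference shrinks. The stake is an understated early effect, not a false positive.

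**Working it through.** The plan gives no figure on this point to reproduce, so the check is an enumeration.

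**Inputs.** Visit 3 is on study day 7 ± 2, that is Days 5 to 9 (Protocol Appendix 2). GPSS is daily; GPSIS and SFQ are weekly (same table). Windows, baselines and recall periods are as set out above.

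**Assumptions not in the documents.** Diaries are complete, weekly entries are exactly 7 days apart, weekly entry days are spread evenly relative to dosing, and the Day 1 entry precedes the injection.

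**1. GPSS.** With Visit 3 on Day v, the window runs from Day max(1, v − 7) to Day v − 1. If it contains Day 1, that entry's share is 1/n, where n is the number of days in the window.

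| Visit 3 | Window | n | Day 1 share |
|---|---|---|---|
| Day 5 | Days 1–4 | 4 | 1/4 = 25% |
| Day 6 | Days 1–5 | 5 | 1/5 = 20% |
| Day 7 | Days 1–6 | 6 | 1/6 = 17% |
| Day 8 | Days 1–7 | 7 | 1/7 = 14% |
| Day 9 | Days 2–8 | 7 | 0% |

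Calendar Week 1 gives 1/7 = 14%. Because at least 4 scores are needed, the share never exceeds 25%, even with incomplete diaries. If Day 1 carries no drug effect, the retained difference is 1 − share: 5/6 = 83% at the nominal Day 7.

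**2. Weekly scales, Visit 3 on Day 7.** An entry counts if made on Days 1 to 6. Of the 7 days before an entry on Day d, 8 − d precede Day 1: 7, 6, 5, 4, 3 and 2 of 7 for d = 1 to 6. The mean is 27/42 = 64%. If the entry day itself counts as a recall day, the number is 7 − d and the mean is 21/42 = 50%. For Visit 3 on Day 5 and Day 9 the means are 79% and 43% on the first convention, 64% and 31% on the second. The Day 1 entry is the one scored for 1 of 7 diary schedules when Visit 3 is on Days 5 to 8, and for none on Day 9, where the Day 8 entry supersedes it.

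**3. How much of the weekly dilution comes from the opening date.** Removing Day 1 leaves entries on Days 2 to 6:

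- first convention: (6+5+4+3+2)/35 = 20/35 = 57%, down from 64%;
- second convention: (5+4+3+2+1)/35 = 15/35 = 43%, down from 50%.

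Most of it therefore stays. It comes from a 1-week recall at a visit one week after dosing.

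**4. What moving the opening to Day 2 costs.** GPSS entries become 3, 4, 5, 6 and 7 for Visit 3 on Days 5 to 9, so the 4-entry minimum fails on Day 5. For the weekly scales with Visit 3 on Day 7, schedules with no eligible entry rise from 1 of 7 to 2 of 7.

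**5. Link to Week 12.** Week 12 SFQ and GPSIS scores are those collected on site at Visit 7, and the Week 12 GPSS average ends on that visit. None uses the Week 1 window. The SFQ Item 2 baseline does select patients for the fourth test in the SAP sequence (baseline at least 2). A patient whose weekly entry falls on Day 1 before dosing is classified on a value about a week older. Under even spacing that is at most 1 patient in 7.

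**The case against.** The strongest reply is that the date cut is deliberate and safe. The general baseline rule in 6.1.2 yields to specific rules, and the SAP revision history lists the diary baseline as an addition. A cut by date keeps any post-dose Day 1 entry out of baseline. The documents give no clock times for diary entries. The requirement in Protocol 8.1.2.2.1 to complete the GPSS before the clinical examination makes a pre-dose entry plausible without fixing it. The bias is also towards no difference, at time points outside alpha control.

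Most of this stands. A reader might infer that 6.1.2 contradicts itself; it does not, because the diary rule is an allowed exception. A reader might also infer that the early itch analysis over the first 14 days is diluted. Table RHBQ.6.5 specifies it on daily scores, so Day 1 is its own point and is not averaged into later days.

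The reply does not explain why an entry made before the injection should count as post-baseline. Keeping post-dose entries out of baseline does not require scoring pre-dose entries as outcomes.

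**Conclusion.** The point holds for Day 1 entries. The Day 1 score is 14% to 25% of the GPSS Week 1 average for Visit 3 on Days 5 to 8 with full diaries, and one seventh of Calendar Week 1. A GPSIS or SFQ entry made on Day 1 before dosing is scored as an outcome although it is pre-dose throughout and is the freshest baseline value. The direction is towards zero.

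Three stronger readings are not supported:

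- **That every Week 1 result is diluted by the window.** With full diaries and Visit 3 on Day 9, GPSS is untouched.
- **That the opening date explains the weekly scales' pre-dose content.** Entries on Days 2 to 6 carry it because of the 1-week recall.
- **That the alpha-controlled tests are compromised.** Their outcomes are Week 12 scores. The only link is an older pre-dose SFQ value in the baseline filter for a minority of patients, under a rule that is the same in both arms.

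The GPSS shares rest on full completion and on Day 1 being untreated. The weekly figures rest also on evenly spread diary days and on the recall convention chosen.

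**What to change.** - **GPSS, Table RHBQ.6.4.** Start the Week 1 window and Calendar Week 1 on study day 2. Use the entry dated on Visit 3 only when it is needed to reach 4 scores (Days 2 to 5 when Visit 3 is on Day 5). In that case leave it out of the Week 2 average, whose window currently opens on the previous visit date.
- **Baseline, 6.1.2 and Table RHBQ.6.4.** Let a Day 1 entry time-stamped before the injection serve as the GPSIS or SFQ baseline and be eligible for the GPSS baseline average. Never score such an entry as Week 1 or Calendar Week 1.
- **Reporting.** Keep the Week 1 and Calendar Week 1 GPSIS and SFQ results, label them as largely pre-dose recall, and name Week 2 as the first interpretable time point for these scales.

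The cost is SAP wording and derivation code, and it depends on diary time stamps being available. A few more Week 1 scores become missing, and under NRI these count as non-response. Dropping the weekly scales' Week 1 results altogether would be a trade-off, since it removes prespecified time points; labelling them is enough.
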